The study phone number will also be used to send the text messages that provide participants with access to their randomly assigned materials. For participants assigned to the control condition, the study phone number is where the link to the playlist of CDC videos will be sent. This text will originate from the study coordinator’s project phone. For participants assigned to receive the **Shine** intervention, their “join” text will launch a check of the originating number against the study phone numbers in the data file. A request from a phone number not in the data file will be denied. This will ensure that no one other than participants assigned to receive the **Shine** intervention can access it.

To ensure the security of this personal information, all **Shine** study phone numbers will be encrypted and stored on a secure server, behind a firewall. Further, texts and active web links will be sent through a secure communication protocol HTTPS to the SMS text messaging gateway, and then on to participants’ phones. This protocol protects against malicious third parties attempting to access the phone number data while information is being transferred from the SMS software application to participants’ phones. All participant phone numbers will be deleted from the secure server upon completion of the field test (experimental participants) or post-study **Shine** access (control participants). Experimental group participants will complete assessment items and receive personalized feedback as part of the **Shine** intervention. A database hosted on separate server from the web application will contain a list of SMS-based replies for each response option from the assessment. Receipt of one of those response options will trigger a tailored SMS response.

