Consent forms will be signed electronically. A password-protected excel spreadsheet (called the Contact File) will contain participants' contact information (i.e., first and last names, study phone number, secondary phone number, email address and/or mailing address based on payment preference) and a log of the time, date, and content of all interactions with participants. Further, a single linkage file will be maintained that links participant names to user ID numbers. No names will be included on the survey and only the ISA Principal Investigator and the study coordinator will have access to the linkage file. The linkage file will be stored separately from the survey data on a password-protected computer, in a password protected Excel file. Importantly, staff at TWOCC will not have access to the research survey data. In addition, no one outside the research team will have access to any information with personal identifiers and ISA will not report any data with personal identifiers.

13. Indicate how potential subjects will be identified and recruited for participation in the study:

Given the size and hard to reach nature of our target population, multiple strategies will be used to recruit participants. All recruitment will be conducted by the Trans Women of Color Collective (TWOCC). TWOCC is a national organization designed to “uplift the narratives, leadership, and lived experiences of trans people of color.” A key component of these efforts is hosting and participating in events throughout the country that are designed to offer support and empowerment to African American trans women. These events include happy hours, networking and leadership seminars and retreats, art showings, activism, national and international speakers, fashion shows, and dance parties. TWOCC also uses social media to reach and connect with trans women of color throughout the country. All recruitment will be passive, with the two main recruitment strategies being in-person and online.

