15. Indicate how you will determine whether the subjects (or their surrogates) understand the information that was provided in the consent document:

All participants will be given the opportunity to ask questions after the study coordinator has explained the study and before they receive the informed consent text message. In addition, after reviewing the informed consent, participants will be asked again if they have any questions or want more information on any aspect of the study. Finally, all participants will be provided with the names and phone numbers of the study PI and the ISA IRB. They will be instructed to call the PI or ISA if they have questions related to requirements of participation or for questions related to the nature of the study.

16. Summarize in a narrative what actually will be done to the subjects during their participation in the study.

(A) a clear description of what is being done for research purposes and what is being done as part of standard clinical care;

All described procedures, including the completion of research surveys, the **Shine** program, and the control videos, are part of the research process. The study procedures will take place over a 6-month period. First, all consented participants will complete the baseline research survey via telephone (see Appendix D: Research Surveys), be randomized to the experimental or control condition, and review their assigned materials (either the **Shine** program or a YouTube playlist of CDC-developed videos on HIV prevention and treatment among transgender adults). While the **Shine** intervention is designed to be completed in 1-2 months, participants will have up to 3 months to complete the intervention. Three months after sending the “join” text, experimental participants’ access to **Shine** will be terminated. Six months after the first research appointment, all participants will again be contacted by phone to complete the follow-up survey. After completing the follow-up survey, participants in the control condition will have access to the **Shine** program. Please see Appendix E: Study Protocol for more information on these procedures. In addition, please see Appendix F: Reminder Protocol and Appendix G: Retention Protocol for details on additional contact with participants.

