(B) a list of tests and procedures that will be performed for research purposes (e.g. blood tests, urine tests, cultures, interviews, questionnaires, surgical procedures, cardiac catheterization, pulmonary function tests, X-rays, scans, etc.);

Please see Appendix D: Research Surveys for all research items.

(C) a brief description of the analyses that will be performed on the biologic or non-biologic (i.e. questionnaires) samples collected

The data will derive from a randomized controlled trial (RCT) with random assignment of individual participants to one of two study conditions (intervention vs. control). Data will be collected at baseline and at 6 months post-baseline. The primary outcome measure is a binary composite HIV transmission risk score. This dichotomous metric is calculated by measuring whether a participant or her partner consistently used at least one effective method for reducing HIV transmission risk (i.e., adherence to biomedical [ART or PrEP] and behavioral [condoms, serosorting] strategies) during each instance of anal sex over the past month. Every anal sex act must be protected by one of these methods to receive an overall composite score of 0. The individual behavioral components of the composite score (i.e., percentage of condomless anal sex, serosorting, PrEP or ART adherence) will serve as secondary measures. In addition, specific outcomes by HIV status will include HIV medical care utilization and adherence, HIV testing, and PrEP knowledge, interest, and uptake. Finally, further secondary measures will assess gender affirmation, well-being, social support, and sexual communication. All measures are self-report and assessed using established scales that have evidence of reliability and validity.

Binomial logistic regression will be the main analytic technique for the primary outcome (composite HIV transmission risk score) and other non-continuous measures. For continuous measures, hierarchical linear modeling (HLM) will be used. All models will control for any demographic covariate (e.g., age) that varies at the .2 significance level due to randomization failure at baseline.

(D) a list of investigational devices that will be used, indicate if they are classified as significant risk (SR) or non-significant risk (NSR) devices and whether there is an IDE or there is an application to the FDA for an IDE if the device is SR;

N/A

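### Does the 6-month telephone survey need a stated caller and masking rule to protect the self-reported primary outcome?

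*Combined protocol and SAP*

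**What the plan says.** Item 16(A) has both surveys done by telephone and, for the second, states only that "all participants will again be contacted by phone to complete the follow-up survey". No role is named, and masking of callers, coordinator or analysts is not mentioned anywhere in the document. The same paragraph adds "Please see Appendix E: Study Protocol for more information on these procedures", and points to Appendices F (reminders) and G (retention) for other contact with participants. None of the three is in the public text.

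Item 16(C) defines the primary outcome as a binary composite over the past month: "Every anal sex act must be protected by one of these methods to receive an overall composite score of 0". It adds: "All measures are self-report and assessed using established scales that have evidence of reliability and validity".

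Two items bear on who could know the arm. Item 10 describes how controls are texted the link to their videos: "This text will originate from the study coordinator"'s project phone. Item 12 says the Contact File holds the study phone number together with "a log of the time, date, and content of all interactions with participants". Item 12 also says that "only the ISA Principal Investigator and the study coordinator will have access to the linkage file". That limit covers the file joining names to user IDs, not the Contact File.

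**The concern.** A self-reported outcome on sexual behaviour and medication adherence, taken by voice, is open to influence from the person asking. A caller who knows the arm might probe, clarify or record differently for Shine users and controls. Randomisation gives no protection, because the difference arises at measurement. It would appear in the logistic regression as an effect of Shine, and the document describes no biological measure that could check the answers.

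The concern also has a concrete basis. The coordinator is the role named for collecting the study phone number (item 10), explaining the study and staying on the line during consent (items 14 and 15), and sending controls their link (item 10). If the same person makes the 6-month call, that caller knows at least who the controls are. Anyone else who works from the Contact File could find the control link text in the log. The safeguards in items 16(C) and 16(F) are careful wording, freedom to skip, names kept off responses, items already used in similar populations and established scales. None of them bears on the caller's knowledge of the arm.

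**Working it through.** The plan gives no figure on this point to reproduce. The check has two parts.

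**1. What has to be true for bias to arise**

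| Link | What the document shows |
|---|---|
| (a) The caller is the coordinator, or uses the Contact File | Not stated. Phone numbers in the survey data file are encrypted (item 10), which makes the Contact File a plausible source, but that is inference |
| (b) The log reveals the arm | Supported: the log covers all interactions (item 12), and the control link is a text from the coordinator's phone (item 10) |
| (c) The caller knows the arm when asking the questions | Follows if the coordinator calls; otherwise the caller must have read the log. Neither is stated |
| (d) The caller prompts or records differently by arm | Nothing in the document bears on this |

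Only (b) has direct textual support. The form's item 16(A) asks what is done for research and what is standard care; it does not ask about staffing or masking. Silence there, beside a pointer to a fuller procedures document, says little about whether the trial has a rule.

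**2. How much a caller effect could matter**

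From the document: 215 participants and two arms. Assumed, because the document gives no allocation ratio, event rate, retention or significance level: 1:1 allocation (107 control, 108 Shine), no true effect, two-sided 5% test, and true past-month risk of 40% to 70%. A pooled two-proportion z-test stands in for the planned logistic regression. The caller is assumed to turn a fraction u of true risk reports in the Shine arm into no-risk reports, and none in the control arm.

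- Reported risk: control p, Shine p(1 − u); difference d = pu
- SE0 = √[p̄(1 − p̄)(1/107 + 1/108)], with p̄ the pooled proportion; SE1 is the unpooled equivalent
- P(reject) = Φ[(d − 1.96·SE0)/SE1] + Φ[(−d − 1.96·SE0)/SE1]

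| p | u | Control v Shine | d | SE0 | P(reject) |
|---|---|---|---|---|---|
| 0.40 | 1% | 0.400 v 0.396 | 0.0040 | 0.0668 | 2.9% + 2.2% = 5.0% (before rounding) |
| 0.40 | 2.5% | 0.400 v 0.390 | 0.0100 | 0.0667 | 3.5% + 1.7% = 5.3% (before rounding) |
| 0.70 | 1% | 0.700 v 0.693 | 0.0070 | 0.0627 | 3.2% + 1.9% = 5.1% |
| 0.70 | 2.5% | 0.700 v 0.6825 | 0.0175 | 0.0630 | 4.6% + 1.3% = 5.9% |

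SE1 equals SE0 to three decimals in each row. In numbers of women, the range runs from 108 × 0.40 × 0.01 = 0.4 to 108 × 0.70 × 0.025 = 1.9 reclassified in the Shine arm. Under-reporting that is equal in both arms leaves the rate at 5.0%.

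These values of u are assumptions, not estimates. At u = 5% (2.2 to 3.8 women) the same formula gives 6.0% to 8.5%, so the result depends wholly on a quantity that the document cannot supply.

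**The case for a change.** The strongest opposing case is that the gap is real and cheap to close. Readers of the result will want to know whether the assessor was masked, and the public text cannot tell them. A sentence naming the caller, and a call list without the arm or the log, would cost little. The caller's influence might also exceed the 1% to 2.5% assumed above. A single act can decide the composite, and one misreport of PrEP or ART adherence could flip it.

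Part of this stands. The text is silent, and a caller could know the arm. The rest is weaker. Naming the caller, or stating that the caller is unmasked, improves the description but changes neither the data nor the analysis. Masking would change the data, but it may need another member of staff. That person could not hold the link between names and user IDs, which item 12 keeps to two roles, yet would have to reach the right woman for a sensitive call and file her answers correctly.

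The gain would also be partial. Participants know what they received and can say so on the call. Item 10 adds a further arm-specific influence: "Experimental group participants will complete assessment items and receive personalized feedback as part of the" Shine intervention. That may shape later answers whoever asks the questions. Nor is the composite equally fragile in both directions: a woman with several unprotected acts still scores 1 if she leaves out only some of them.

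**Conclusion.** No change to the plan follows. The public summary does not name the 6-month caller or say whether that person is masked. That is missing detail in a form that defers these procedures to Appendices E to G, and it does not show that the trial is unmasked or that answers would differ by arm. The study team can settle the question from those appendices, and the trial report would ordinarily state whether the survey caller was masked.

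The document gives no basis for estimating a caller effect. Under the stated assumptions (107/108, no true effect, true risk 40% to 70%, two-sided 5% test), a caller-only under-reporting of 1% to 2.5% in the Shine arm gives a false-positive rate of 5.0% to 5.9%. A larger caller effect would matter more, but nothing in the text points to one. Bias from participants knowing their own arm is a separate matter, which masking the caller would not cure. The judgement would change if the appendices showed a caller working with the arm in view when staff who did not know it could have made the call.

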(E) a statement that defines who will be financially responsible for the costs associated with participation in the study (e.g. examinations, procedures, drugs, devices, etc.) and a statement that defines what will be provided without cost to the subjects;

ISA will be responsible for all costs. Participants will be provided access to the **Shine** program and up to \$175 in cash incentives.

(F) your assessment of whether the research involves any physical, psychological, social and/or economic risk(s) and the magnitude of the risk(s);

We believe that the potential risks of collecting the survey data are small. It is possible that as a result of completing the research survey questions, a participant may learn that her behavior puts her at risk for negative HIV-related outcomes (i.e., contracting HIV or worsening disease, depending on status). This realization may be accompanied by distress. If this should occur during survey administration, participants will be encouraged to discuss their concerns with a health care provider. They will also be provided with a list of resources in the informed consent that can provide information about HIV. Further, a participant may become uncomfortable when responding to questions regarding her health history. To minimize this risk, the questions will be phrased in ways to minimize any potential discomfort and participants will be free to skip any question they do not wish to answer. Further, the research team is using survey items that have been successfully used in past research with similar populations. Finally, users will complete the surveys via telephone call and their names will never be associated with their survey responses. These confidentiality measures should also serve to reduce any potential risk to participants.

We also believe that the potential risks of going through either the experimental or control conditions are small. It is possible that, as a result of reviewing either the **Shine** or control materials, a participant may learn that her behavior (e.g., inconsistent adherence to ART; condomless anal sex) may put her at risk of poorer HIV-related outcomes. These realizations may be accompanied by distress. If this should occur, participants will be encouraged to discuss their concerns with a health care provider. The informed consent will also provide information on alternative methods for receiving the type of information available in the **Shine** intervention and control materials.

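### Does collecting the self-reported primary outcome on a telephone call, rather than by private self-entry, weaken the trial?

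*Combined protocol and SAP*

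**What the plan says.** Item 16(A) sets the mode at both time points. At entry "all consented participants will complete the baseline research survey via telephone", and six months after the first research appointment "all participants will again be contacted by phone to complete the follow-up survey". For detail it adds: "Please see Appendix E: Study Protocol for more information on these procedures". Neither that appendix nor Appendix D, which holds the survey items, is in the available text.

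Item 16(C) defines the primary outcome. It asks whether an effective method (ART or PrEP adherence, condoms, serosorting) was used by the participant or her partner "during each instance of anal sex over the past month". The rule is strict: "Every anal sex act must be protected by one of these methods to receive an overall composite score of 0". On the source of the data: "All measures are self-report and assessed using established scales that have evidence of reliability and validity".

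Item 16(F) treats the mode as part of the protection of participants: "users will complete the surveys via telephone call and their names will never be associated with their survey responses". Its next sentence counts these arrangements as confidentiality measures that should lower risk. The same item promises careful wording and items already used with similar populations, and says that "participants will be free to skip any question they do not wish to answer".

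**The concern.** The composite turns on a single act: one unprotected act left unreported changes a score of 1 to 0. The available text describes no biological or record-based check, so the main result rests on candour. Items 1 and 2 describe a population facing discrimination and marginalisation, and a woman may hesitate to tell a staff member about condomless sex or missed medication. Careful wording and keeping names off the stored responses do not make a spoken answer private from the person on the call.

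Two consequences are possible:

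- **Equal under-reporting in both arms** shrinks a real difference and costs power. The planned logistic regression cannot restore it.
- **Greater under-reporting in the Shine arm** would bias the result toward Shine.

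An alternative seems close at hand. Item 14 already texts a link to a secure consent page while the coordinator stays on the line, and Item 5 requires a smartphone and the ability to read English. The sensitive items could be typed in the same way during the same calls.

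**Working it through.** **What the documents supply.** The total of 215 (Item 3) is the only design figure. There is no allocation ratio, event rate, effect size, power, misreporting rate or skipping rate. So no figure in the plan can be reproduced or contradicted here, and everything below is illustration under stated assumptions.

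**Equal under-reporting.** Assume 1:1 allocation (n = 107.5 per arm), all 215 analysed, a two-sided 5% pooled test of two proportions, and control risk of .60 or .70. Power is Φ((d − 1.96·s0)/s1), where s0 = √(2p̄(1−p̄)/n) and s1 = √([p1(1−p1)+p2(1−p2)]/n). The true difference with 80% power is .190 (control risk .60) or .186 (.70). If a share u of at-risk women in both arms under-report, each risk is multiplied by (1−u).

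Worked case, control risk .60 and u = .10:

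- p1 = .60 × .9 = .540, p2 = .41 × .9 = .369, d = .171
- s0 = .0679, s1 = .0669
- (.171 − 1.96 × .0679)/.0669 = .566, so power = .714

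Suppose self-entry removes a quarter or a half of the under-reporting. The last column is the extra share of missing composites, applied as n(1−m) and assumed unrelated to risk, at which power falls back to the telephone value. Each cell gives control risk .60 / .70.

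| u by phone | Power by phone | Removed | Power with self-entry | Break-even extra missing |
|---|---|---|---|---|
| 5% | .758 / .748 | quarter | .769 / .761 | 2.5% / 3.1% |
| 5% | .758 / .748 | half | .779 / .774 | 5.0% / 6.1% |
| 10% | .714 / .694 | quarter | .737 / .721 | 5.0% / 6.0% |
| 10% | .714 / .694 | half | .758 / .748 | 9.7% / 11.7% |
| 20% | .624 / .587 | quarter | .669 / .640 | 9.9% / 11.5% |
| 20% | .624 / .587 | half | .714 / .694 | 18.7% / 21.7% |

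At u = 10% the gain is about 2 to 5 points, and it is lost once some 11 to 25 of 215 women have a composite missing that a call would have completed. At 5% the gain is about 1 to 3 points, and at 20% about 5 to 11. If self-entry removes nothing and 5% more composites go missing, power at u = 10% falls to .692 / .671. The documents do not say which row applies.

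**Unequal under-reporting.** With no true effect and a true risk of .60, an extra 10% under-reporting in the Shine arm alone would raise the rejection rate from 5% to 14.4%. That bias comes from a woman knowing which materials she received. Typing her answer does not remove that knowledge, so this figure cannot be credited to a change of mode.

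**Prior disclosure.** Item 5 admits only women who report condomless anal sex together with inconsistent ART or PrEP use, and Item 13 routes screening through the study coordinator. If screening is spoken, as Item 14 suggests, every enrolled woman has already told staff about such behaviour.

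**What self-entry would cost.**

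- Some women would need items read aloud, since Item 8 expects educationally disadvantaged participants. The primary outcome would then be mixed-mode, with mode probably related to education.
- The composite covers every act in a month, several methods, and the partner's behaviour as well as the participant's. An interviewer can clarify this; a web form may not.
- Item 10 treats sensitive content on the phone as a privacy matter and offers to show Shine users how to erase messages. A sexual-behaviour form on that phone raises the same issue.
- Self-entry would not mask staff. Under Item 10 the control link is sent from the coordinator's own project phone.

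**The case for a change.** The strongest contrary case is that the exposure falls on the primary outcome, cannot be repaired in analysis, and could be reduced cheaply with a texting step already in use. Disclosure at screening is also not the same as disclosure at follow-up. Reporting risk at screening gains entry to the study. The six-month answer concerns a later month, after materials that may have taught the woman that her behaviour is risky.

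Part of this stands. The outcome is wholly self-reported, a live spoken answer is the likely reading of a telephone call, and candour may differ at follow-up. But pressure that arises after seeing the assigned materials is the very part that self-entry may leave in place. That speech produces more under-reporting than typing here is plausible, but it is an outside premise that the documents neither state nor quantify. Cheapness does not settle the matter when the net effect on power could go either way.

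**Conclusion.** The concern does not hold. No rule, figure or analysis in the plan is wrong. The telephone is an open choice, presented as a confidentiality measure and applied alike in both arms at both surveys, so the mode by itself creates no false benefit. Under the assumptions above, a plausible gain of a few points of power from self-entry is cancelled by a modest rise in missing composites: about 5 to 12% at 10% under-reporting, and about 2.5 to 6% at 5%. Higher under-reporting would favour self-entry more, but no rate is given, and skipping of sensitive items may well depend on risk, which the calculation ignores. The alternative also brings mixed modes, loss of clarification and a privacy cost on the phone. Experienced statisticians could reasonably choose either mode. The conclusion rests on the available text; Appendices D and E may describe the call in more detail.

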We intend to meet this unfulfilled need by developing **Shine**, a mobile intervention designed specifically for African American TGW that is theory-based, individually-tailored, and empowering. Based on the IMB-model, users receive three types of personalized text messages: informational, motivational, and skill-building. Based on the Model of Gender Affirmation, additional messaging provides strategies for gaining intra- and interpersonal forms of gender affirmation. These text messages are supplemented by two types of web-based videos: unscripted peer narratives and educational instruction. Links to these videos are integrated into the messaging to enhance the trans-specific understanding of gender affirmation within our IMB framework.

We plan to test the effectiveness of **Shine** in a randomized controlled trial with 215 African American TGW. Participants will be randomly assigned to receive either the mobile **Shine** intervention or a YouTube playlist of CDC-developed videos about HIV for transgender adults. Before and at 6-months post-randomization, we will assess participants' risk for HIV transmission, practice of individual recommended behaviors based on HIV status (i.e., condomless anal sex, ART adherence, PrEP interest/uptake), barriers to those behaviors, gender affirmation, and social support.

3. Indicate the total number of subjects and the number of sites:

Number of subjects: 215

Number of sites: 1 (1 recruitment partner [Trans Women of Color Collective], with recruitment occurring in person and online throughout the United States)

4. Indicate the characteristics of study population:

(a) Gender: Males yes no X

Trans Females yes no _____

(b) Age range: from 18 to no upper limit

(c) Racial and Ethnic Groups:

| | | |
|------------------------|---|--|
| Caucasian | yes _____ | no  _____ |
| Black | yes  _____ | no _____ |
| Hispanic | yes  _____ | no _____ |
| American Indian | yes _____ | no  _____ |
| Alaskan Native | yes _____ | no  _____ |
| Asian/Pacific Islander | yes _____ | no  _____ |
| Other (specify) _____ | | |

(d) Justify any exclusion of specific gender, age, and racial or ethnic groups:

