Shine, the proposed intervention program, is specifically aimed at TGW. Approximately 20% of TGW in the United States are infected with HIV. While Black TGW make up only 16% of the U.S. population of TGW, they account for over half of new HIV infections. Because of this burden, and the dearth of effective, broadly disseminated interventions targeting African American TGW, **Shine** is designed specifically to improve HIV outcomes and increase access to gender affirmation in an African American population. To provide a meaningful test of this program's efficacy, only African American participants will be included in the randomized controlled trial of **Shine**.

Children will not be included in the proposed randomized controlled trial. While children younger than 18 represent an important group for HIV prevention and treatment efforts, their developing physical, cognitive, and social-emotional skills and capacities require unique HIV planning separate from adults. As such, recruitment will be limited to adults.

5. State inclusion criteria for enrollment in study:

To be eligible, participants must: 1) identify as a Black transgender woman using the recommended 2-step method (Step 1: assigned male birth sex, Step 2: current gender identity is female); 2) be aged 18 or older; 3) report risk of HIV transmission in the past 3 months (i.e., condomless anal sex with a serodiscordant or risky male partner and either inconsistent ART adherence or inconsistent PrEP use); 4) own a smartphone; and 5) be able to read and speak English.

6. State exclusion criteria for enrollment in study:

The only exclusion criterion for this project is the failure to meet the inclusion criteria described above.

7. Will vulnerable subjects be enrolled in this study? yes no _____

| | | |
|--|---|--|
| (a) Individuals with diminished mental capacity | yes _____ | no  _____ |
| (b) children | yes _____ | no  _____ |
| (c) pregnant women | yes _____ | no  _____ |
| (d) fetuses | yes _____ | no  _____ |
| (e) economically or educationally disadvantaged persons | yes  _____ | no _____ |
| (f) prisoners | yes _____ | no  _____ |

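### Do the component secondary outcomes need a written scoring rule for women with no ART/PrEP use or no anal sex in the month?

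*Combined protocol and SAP*

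**What the plan says.** Item 16(C) defines the primary outcome as a yes/no composite that records "whether a participant or her partner consistently used at least one effective method" to reduce transmission risk "during each instance of anal sex over the past month". A woman scores 0 only if all her acts were covered. The components, "percentage of condomless anal sex, serosorting, PrEP or ART adherence", are then listed as secondary measures with no scoring rule of their own. Further outcomes depend on HIV status and include "PrEP knowledge, interest, and uptake". On the models it says: "For continuous measures, hierarchical linear modeling (HLM) will be used". Non-continuous measures go to logistic regression. The same item says that all measures are self-reported and come from established, validated scales. The survey items are in Appendix D, which is not part of the available text.

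Two other places bear on the point. Item 2 links the behaviours assessed ("condomless anal sex, ART adherence, PrEP interest/uptake") to the participant's HIV status. Item 5 requires that women "report risk of HIV transmission in the past 3 months", defined as condomless anal sex with a serodiscordant or risky partner together with "either inconsistent ART adherence or inconsistent PrEP use".

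**The concern.** Two groups of women have no obvious value on a component. The first is women not taking ART or PrEP. PrEP uptake is an outcome in its own right, so some HIV-negative women are presumably off PrEP at entry. The second is women with no anal sex in the scored month. Entry looks back three months and the composite one month, and nothing requires any acts at 6 months, so the condomless percentage can be 0/0.

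If these records were treated as missing, adherence would be compared among users only. Being a user at 6 months is something the trial measures as a possible effect of Shine, so the comparison would condition on a post-randomisation state. An arm difference could then appear, in either direction, only because different women entered the denominator. The same holds for the condomless percentage if Shine changes who is sexually active. It is also unstated whether adherence covers the participant only or, as in the composite, her partner too. What is at stake is the reading of which behaviour drives the composite.

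**Working it through.** The plan gives no figure on this point to reproduce. The inputs below are assumed and serve only to show the mechanism.

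**PrEP adherence, users only.** Per 100 HIV-negative women per arm: 20 existing users with mean adherence 60% in both arms, and *k* starters in the Shine arm with adherence *s*. No existing user changes.

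- Shine users' mean = (20 × 60 + *k* × *s*) / (20 + *k*).
- *k* = 15: *s* = 30 gives 1650/35 = 47.1; *s* = 60 gives 2100/35 = 60.0; *s* = 90 gives 2550/35 = 72.9. Against 60.0 in control, the differences are -12.9, 0.0 and +12.9 points.
- *k* = 5: 1350/25 = 54.0, 1500/25 = 60.0 and 1650/25 = 66.0, so -6.0, 0.0 and +6.0.
- In a random-intercept model on both waves, where starters have no baseline record, the arm-by-time term is (1 - ρ) × (Shine users' mean - 60). For *k* = 15 and *s* = 30 this is -9.6 at ρ = 0.25, -6.4 at 0.50, -3.2 at 0.75 and -0.6 at 0.95.

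**The same women, non-use scored as not adherent.** Control: 20 × 60 / 100 = 12.0%. Shine, *k* = 15: 1650/100 = 16.5%, 2100/100 = 21.0% and 2550/100 = 25.5%. The differences are +4.5, +9.0 and +13.5 points. Everyone is counted, so there is no selection. The contrast now carries uptake and adherence together.

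**Condomless percentage.** Suppose 10% of control and 20% of Shine women have no anal sex. The extra 10% would have been at 30% condomless and the rest are at 70%.

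- Active women only: control (0.1 × 30 + 0.8 × 70) / 0.9 = 59/0.9 = 65.6; Shine 70.0; difference +4.4.
- No sex scored 0: control 59.0; Shine 0.8 × 70 = 56.0; difference -3.0.

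The scoring rule can therefore change the sign. The users-only or active-only shift is zero if the share and mix of these women are equal by arm, or if starters or leavers resemble the rest.

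**What the text implies about each case.**

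1. *PrEP non-use.* An HIV-negative woman appears able to meet item 5 only through its PrEP clause. If non-users are enrolled, as the uptake outcome suggests, non-use must count there as inconsistent use, and scoring it as not adherent applies the same construct. If non-use does not count, non-users are not eligible, and a cohort with 80 of 100 women off PrEP at baseline cannot arise. Some could still stop by 6 months, but a woman who has stopped is also naturally scored as not adherent.
2. *In whom.* Items 2 and 16(C) tie outcomes to HIV status, which points to ART adherence in HIV-positive women and PrEP adherence in HIV-negative women.
3. *No anal sex.* For the composite, a woman with no acts has no unprotected act, so the rule implies 0. This is an inference from the rule. For the percentage, the ordinary meaning is a share of acts among women with acts.
4. *Visibility.* PrEP uptake is reported as its own outcome, so a shift such as 20 versus 35 users per 100 would be seen beside any users-only result.

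**The case for a change.** The strongest contrary case is that the omission is real, cheap to close and better closed before data are seen. An analyst free to choose between users-only and all-women scoring could choose after looking, and the examples show that the choice can reverse the sign. The mixed model shrinks the users-only shift without removing it. The 0/0 case for condomless sex has no default as natural as the one for adherence. Appendix D is described as holding survey items, which need not include derivation rules.

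Some of this stands. The rule is not written in item 16(C), and the arithmetic follows from its assumptions. But the harm needs a step the plan does not take, namely leaving these records missing. Item 16(C) answers a request for a brief description, so the absence of item-level derivations is expected there and does not show that none exist. All-women adherence scoring is not a correction of users-only scoring. It is a different estimand: under the assumptions above its +4.5 to +13.5 points come entirely from starters, and it overlaps with the uptake outcome already listed. Writing it in would settle a preference and repair no error.

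**Conclusion.** No change to the plan follows. Item 16(C) leaves unstated how non-use of ART or PrEP and a month without anal sex are scored in the component measures, and whether a partner's use counts. No stated rule gives a wrong result. The sensible completions are close at hand: non-use counts as not adherent, and the condomless percentage is taken among women with acts and labelled as such in the report. Appendix D or the established scales may already settle these points.

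The size cannot be derived from the documents. The users-only shift of up to 12.9 points and the condomless shift of 4.4 points rest wholly on assumed shares and adherence levels, and both are zero when the arms do not differ in who uses PrEP or who is sexually active. No figure can be given for serosorting. Only secondary outcomes are touched. The primary composite is unaffected, on the reading that a woman with no acts scores 0. The conclusion would be weaker if the scoring documents turned out to discard non-users without saying so.
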